Transesophageal echocardiography (TEE) to guide and confirm epidural catheters in pediatric patients

NCT Number: 02415998

[name]

Document Date: July 12, 2012

Transesophageal echocardiography (TEE) to guide and confirm epidural catheters in pediatric patients

PI: [name]

IRB ID #: 201207769

Form Content

I. Project Introduction

I.1 Project to be reviewed by:

IRB-01

I.2 Project Title:

Transesophageal echocardiography (TEE) to guide and confirm epidural catheters in pediatric patients

I.3 Short Title (optional):

I.4 Provide a short summary of the purpose and procedures of the study proposed in this IRB application.

DO NOT include information on studies not proposed in this application.

Use LAY terminology only. This must be easily understandable by IRB community members and nonscientists.

DO NOT cut and paste technical abstracts from funding applications that may not be understood by a general audience.

The aim of this study is to assess whether transesophageal echocardiography (TEE) can be used to successfully guide an epidural catheter to a targeted thoracic level in pediatric patients. The catheter will be placed in the epidural space under real-time TEE imaging and assistance by a trained TEE operator (this could include an anesthesiologist or cardiologist).

I.5 Specify your research question(s), study aims or hypotheses (do not indicate "see protocol")

The primary outcome is to determine the success rate achieved using TEE guidance to thread an epidural catheter to a targeted thoracic spinal level. Post-operative radiograph will be used to confirm catheter position.

The secondary outcomes include analysis of catheter tip position within the epidural space as anterior, lateral or inferior to the spinal cord. Further, efficacy of the catheter will be determined using the following criteria from previous studies [1]: Hemodynamic response at skin incision analyzed by heart rate and systemic blood pressure changes using the no change in HR or BP or changes < 20% from baseline were considered "sufficient block" to surgical stimulation, while HR or BP changes > 20% from baseline were considered "not sufficient block" to surgical stimulation.

I.6 Background and significance and/or Preliminary studies related to this project. (do not indicate "see protocol")

Epidural block has been utilized extensively in pediatric patients [2], however, blind advancement of epidural catheters to the thoracic space can be technically

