At this point, the TEE probe will be returned to midesophageal level to visualize the heart and the operation will proceed as usual. Because this study will occur while the patient is being prepared for surgery by the anesthesia team as usual in these surgeries, no additional time in the operating room or catheter laboratory will be required. In fact, it is possible that TEE guidance could decrease time spent under anesthesia and improve confidence in the catheter position. During the procedure, at the time of surgical incision, the anesthesiologist will be asked to note whether the patient exhibits a hemodynamic response to incision. This will be determined by the criteria used in previous studies (Willschke 2006) analyzed by heart rate and systemic blood pressure changes using no change in HR or BP or changes < 20% from baseline were considered "sufficient block" to surgical stimulation, while HR or BP changes > 20% from baseline were considered "not sufficient block" to surgical stimulation. These changes will correlate with the efficacy of the epidural block.

Following surgery, a post-operative x-ray will be taken as is standard procedure to visualize the heart. Because this study will occur only in pediatric patients, the x-ray will also capture and exhibit catheter placement around the spinal cord. This is currently the gold standard confirmatory technique for epidural catheters and this will be used to compare with the success of pre-operative TEE guided catheter placement.

Following all procedures, the success rate achieved by TEE in threading a catheter to the epidural space of targeted spinal levels as compared to confirmation by post-operative x-ray. Further the efficacy of that catheter will be determined with correlation to catheter position (anterior, lateral or posterior to the spinal cord). When looking at patient medical records, we will only collect the following data: height, weight, age, any known history of esophageal abnormalities, lesions or disease, current procedure, hemodynamic markers, FLACC score immediately after surgery when the patient is in the post-anesthesia care unit ** or pediatric intensive care unit ** postoperatively 24 hours after surgery and total morphine used within 24 hours after surgery.

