X.5 ***Do the confidentiality protections indicated above allow only members of the research team to access the data/specimens?***

Yes

X.7 ***Does your study meet the NIH criteria for a [Certificate of Confidentiality](#) or will you be applying for Certificate of Confidentiality?***

No

XI. Data Analysis

XI.1 ***Describe the analysis methods you will use, including, if applicable, the variables you will analyze***

We are planning to determine the success rate achieved using TEE guidance to thread an epidural catheter to a targeted thoracic spinal level. Post-operative radiograph will be used to confirm catheter position for comparison. Thus, we will only use exploratory descriptive statistics for analysis.

XI.2 ***Provide the rationale or power analysis to support the number of subjects proposed to complete this study.***

Because this is a novel technique, we have no base for the ability to use TEE to guide and confirm thoracic epidural catheters. We assume that twenty pediatric patients will provide adequate power to confirm a high success rate for this novel technique in both imaging and guiding the catheter. Therefore, total of 25 subjects will be needed due to account for subjects who may withdraw or become ineligible.

XII. Future Research

XII.1 ***Do you wish to keep any information about subjects involved with this research project so that members of the current research team may contact them in the future for your own research projects?***

No

XII.2 ***Do you wish to keep any information about subjects involved with this research project so that [other researchers](#) may contact them for future research?***

No

XII.4 ***Does this project involve storing any data, tissues or specimens for future research?***

Yes – contribution for future use is mandatory for participation in the study

ROC. Record of Consent

ROC.1 ***Select which option applies to address the University of Iowa Health Care policy [IM-MR-06.21](#) titled "[Documentation of patient participation as a subject in a research protocol or use of an investigational medication,](#)***

study medication, investigational device, or biologic.”

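### Block efficacy is compared across catheter-tip positions only as a yes/no cut at a 20% HR or BP change; the percent change itself should also be recorded and summarised by position

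*Combined protocol and SAP*

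**What the plan says.** Section I.5 names tip position and block efficacy as secondary outcomes. On efficacy it says that "efficacy of the catheter will be determined using the following criteria from previous studies", and it then gives a rule based on HR and BP at skin incision.

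Section VII.E.6 repeats the rule. On one side, "changes < 20% from baseline were considered 'sufficient block' to surgical stimulation"; on the other, "HR or BP changes > 20% from baseline were considered 'not sufficient block' to surgical stimulation". A change of exactly 20% falls in neither class, and no direction of change is given. At incision, "the anesthesiologist will be asked to note whether the patient exhibits a hemodynamic response to incision", which reads as a yes/no entry. The same section lists hemodynamic markers, the FLACC score and 24-hour morphine use among the chart data, but assigns none of them an analysis.

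The link between the two outcomes comes at the end of VII.E.6: "Further the efficacy of that catheter will be determined with correlation to catheter position (anterior, lateral or posterior to the spinal cord".

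Section XI.1 describes only the success rate of TEE guidance and concludes: "Thus, we will only use exploratory descriptive statistics for analysis". No section plans a summary of the percent change in HR or BP by position.

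**The concern.** The label is built from two continuous measurements. Once cut, a 1% change and a 19% change count as the same, while 19% and 21% count as opposites. With about 20 evaluable children spread over three positions, each position may contain very few children labelled not sufficient. A difference between positions could then rest on one or two children.

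At stake is how much the study can say about whether tip position is related to block quality. The percent change comes from the same children and shows more of any such relation. The plan neither commits to summarising it nor says that the numbers behind the label are kept.

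**Working it through.** **Inputs from the documents.** 20 evaluable children (VI.15, XI.2); three tip positions (VII.E.6); a cut at a 20% change in HR or BP (I.5, VII.E.6). The documents give no block failure rate, SD, split across positions, test or significance level for this comparison. XI.2 offers no figure to reproduce here: its statement about adequate power concerns success in imaging and guiding the catheter.

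**Assumptions.** One roughly normal response with equal SD in each position and a one-sided cut; two-sided 5% level where a test is used for illustration. The real rule joins two variables and has no stated direction, so the results are approximate.

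**Step 1: information kept by the cut.** With failure rate p, normal density φ and z_p the normal quantile of p, the large-sample efficiency of the cut relative to the uncut value is φ(z_p)² / [p(1 − p)].

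| Failure rate p | Calculation | Kept | Lost | 20 children count as |
|---|---|---|---|---|
| 50% | 0.399² / 0.25 | 64% | 36% | 12.7 |
| 30% | 0.348² / 0.21 | 58% | 42% | 11.5 |
| 20% | 0.280² / 0.16 | 49% | 51% | 9.8 |
| 10% | 0.175² / 0.09 | 34% | 66% | 6.8 |

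The smallest loss is 36%, at p = 50%. Setting the formula equal to 0.5 gives p ≈ 20.9%, so the loss exceeds half only when fewer than about 21% of blocks fail (or, by symmetry, more than about 79%).

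**Step 2: illustration with two positions, 10 versus 10.** Take sufficient-block rates of 90% and 50%. The matching shift is z(0.9) − z(0.5) = 1.28 SD. Power on the cut, by enumerating all binomial outcomes, is 30% with Fisher's exact test and 47% with an uncorrected chi-square. Power of the exact rank-sum test on the percent change, by simulation, is about 72%. The gap is 72 − 47 = 25 points against chi-square and 72 − 30 = 42 against Fisher. Part of the Fisher gap comes from that test's conservatism at this size, so chi-square is the fairer comparator.

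**Step 3: three positions, split 7/7/6.**

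| Spread of means | ANOVA, uncut | Exact test on the cut, p = 50% / 30% / 20% / 10% |
|---|---|---|
| 1.0 SD | 29% | 17% / 16% / 12% / 5% |
| 1.5 SD | 59% | 35% / 32% / 23% / 9% |

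The uncut scale does better in every row, but even there power is low for a 1 SD spread.

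**Step 4: when a rank-based 95% interval exists.** The smallest two-sided exact rank-sum p-value is 2 / C(n₁+n₂, n₁): 2/20 = 0.10 for 3 versus 3, 2/35 = 0.057 for 4 versus 3, and 2/36 = 0.056 for 7 versus 2. All exceed 0.05, so no 95% interval is available for such splits, which are plausible with 20 children over three positions.

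**The case against.** The strongest reply is that the comparison is secondary and exploratory. XI.1 plans description only, so no test exists whose power could be poor. That stands: a reader might infer that real differences between positions would usually be missed, but this judges a test the plan does not contain. The loss of information remains in a purely descriptive summary, however, and the fix is itself descriptive.

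A reader might also infer that most of the information is thrown away. The documents do not support this. It needs a failure rate below about 21%, and none is given; the high success rate expected in XI.2 concerns imaging and guiding the catheter, not the block. Nor does the plan commit to discarding anything: hemodynamic markers are collected, and XI.1 does not rule out summarising them. The plan is under-specified here. The yes/no wording at incision still leaves it open whether the numbers survive.

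The cut has a purpose: it is an earlier study's criterion for a sufficient block, and it allows comparison with that study. That is a good reason to keep it, but not to use it alone.

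Finally, the main limit is about 20 children over three uncontrolled position groups. That also stands, and a continuous scale does not cure it.

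**Conclusion.** The point holds as a modest, inexpensive improvement. The only efficacy measure named for the comparison across tip positions is a dichotomised one. Under approximate normality the cut costs at least about 36% of the information, and more than half only if fewer than about 21% of blocks fail, which the documents leave unknown. The power figures illustrate that loss under assumed rates and group sizes; they do not describe a planned analysis. Conclusions about position will be weak on either scale, and the primary aim, the success rate of TEE guidance, is not affected.

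**What to change.** In VII.E.6 and XI.1:

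- Keep the sufficient / not sufficient rate at 20%, for comparison with the earlier study.
- State that the numeric baseline and incision values of HR and systolic BP are recorded for every child. The plan speaks of systemic blood pressure without naming the component.
- For each tip position, list the individual percent changes in HR and in systolic BP, with median and range.
- Give a Hodges-Lehmann difference between positions with a 95% interval only where the group sizes allow one, and label it exploratory.

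The cost is a few sentences, two extra descriptive summaries and keeping the numeric values. No extra patient or procedure is needed, because the label already requires a baseline and an incision reading.

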- VII.B.11** *Is there a separate, written protocol that will be submitted in addition to this IRB New Project form? (Note: a grant application is not considered to be a protocol)*
No
- VII.B.18** *Does this project involve testing the safety and/or efficacy of a medical device?*
Yes
- VII.B.19** *Describe in detail procedures in place for maintaining device shipment and receipt records:*
This device is already onsite being used in the UIHC Main Operating Room and Pediatric Catheter Laboratory of alternative purposes, thus, no device shipping or receipt will occur.
- VII.B.20** *Who will be responsible for maintaining these shipment and receipt records?*
N/A
- VII.B.21** *Describe in detail procedures in place for tracking use and disposition of devices described in this study:*
N/A

- VII.B.22 ***Who will be responsible for maintaining these use and disposition tracking records?***
N/A
- VII.B.23 ***Describe in detail procedures in place to limit access to authorized study personnel for the storage, control, and dispensing of the investigational devices. (For example, investigational devices are kept in a locked area away from approved devices or have a keyed interlock, and only study personnel authorized to dispense the device have the keys)***
N/A
- VII.B.24 ***Is the device FDA-approved for the way it will be used in this study?***
No
- VII.B.25 ***Is there an IDE (Investigational Device Exemption) for this device in this research project?***
No
- VII.B.29 ***Indicate the appropriate FDA status you and/or the sponsor are requesting for the use of this device in this study.***
Non-Significant Risk (NSR) device/software
- VII.B.31 ***Provide a detailed rationale for why this device meets the FDA definition of a Non-Significant Risk Device (NSR)***
Because it is not intended as an implant nor is it to be used in supporting or sustaining human life. At this time it is not of substantial importance in diagnosing, curing, mitigating or treating disease.
- VII.B.32 ***Provide a summary of prior investigations with this device.***

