The time period for the pre-operative procedure will require approximately thirty minutes but will not extend patient time in the operating room or catheter laboratory as all procedures will occur as the patient is being prepared for surgery and this would occur normally by the anesthesia team.

No additional visits or extra time is required of the subject. There will be no necessary long-term follow up or data collection. When the patient leaves the operating room, nothing additional is required.

VII.E.7 *Will you attempt to recontact subjects who are lost to follow-up?*

No - followup is not required in this study

VII.E.9 *Will subjects be provided any compensation for participating in this study?*

No

VIII. Risks

VIII.1 *What are the risks to subjects including*

- *emotional or psychological*
- *financial*
- *legal or social*
- *physical?*

The care the patient will receive is standard practice at UIHC for cardiothoracic surgery or interventional cardiology diagnostic procedures under general anesthesia and are necessary procedures regardless of this research study. The postoperative x-ray would occur to visualize the heart, regardless of study participation thus, no additional exposure to ionizing radiation is incurred by participation. The only potential additional physical

risk involved is an increased risk of esophageal trauma as the TEE probe may be maneuvered more than normal to observe catheter entry and anesthetic spread. The low risk of esophageal injury associated with TEE makes this unlikely but it is still a possibility that must be noted. Patients ******(and parents)****** may be under slightly elevated emotional stress knowing that they are part of a research study. There is a very low risk of loss of confidentiality of the patient's medical information, yet this is unlikely as patients will be given identification numbers at the earliest date possible and these will only be accessed by members of the research team. Only the data necessary to answer the research question will be collected upon reviewing patient information. There are no other known financial, physical or legal risks to the patient.

- VIII.2** ***What have you done to minimize the risks?***
If applicable to this study ALSO include:
How you (members of your research team at Iowa) will monitor the safety of individual subjects.

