Include a description of the availability of medical or psychological resources that subjects might require as a consequence of participating in this research and how referral will occur if necessary (e.g. availability of emergency medical care, psychological counseling, etc.)

Healthcare professionals will monitor the subject at all times during the operation. The patient will be reassured that although they are participating in the study, everything that happens during the case is already standard practice at UIHC for cardiothoracic surgery or interventional cardiology diagnostic procedures under general anesthesia. TEE probe maneuvering will only be done as necessary to minimize any physical trauma beyond what is already standard procedure in these patients. All patients will be given an identification number and be referred to by such. To prevent loss of confidentiality of the patient's medical information, we will keep all records used for this study in a locked office or on password protected computer system. Only members of the research team will have access to the records used in this study. No key will be kept as patients will not need to be contacted in the future.

- VIII.3** ***Does this study have a plan to have an individual or committee review combined data from all subjects on a periodic basis (such as summary or aggregate safety and/or efficacy data)?***

No

IX. Benefits

- IX.1** ***What are the direct benefits to the subject (do not include compensation or hypothesized results)?***

There are no direct benefits to the subject.

- IX.2** ***What are the potential benefits to society in terms of knowledge to be gained as a result of this project?***

This novel method to visually confirm epidural catheter placement and anesthetic spread within the epidural space could greatly increase the safety and success rate of epidural analgesia. Further, it provides an alternative to the ionizing radiation and contrast injection used in current methods of fluoroscopy to confirm catheter placement. By determining the success rate achieved using TEE as an alternative method to thread and confirm epidural catheter placement, it will allow us to compare with current techniques already in use and potentially improve patient safety and care.

X. Privacy & Confidentiality

X.1 *What are you doing to protect the privacy interests of the subjects?*

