The research related activities proposed in this study **does meet** the registration requirements under the University of Iowa Health Care policy IM-MR-06.21 titled “Documentation of patient participation as a subject in a research protocol or use of an investigational medication, study medication, investigational device, or biologic.” **The below information must be completed and approved as part of the IRB application. This information contained within this page will be used to create the Epic Research Study Application Form.**

ROC.2 ***Select a publicly viewable title for this study. (This title will be visible in EPIC)***

Release full title

ROC.3 ***Select research team member who has taken Epic Training***

ROC.4 ***Who is a 24/7 contact person for projects involving treatment(s) or procedures that result in complications or side effects?***

[name]

Other contact information that may be relevant to a subject’s clinical care (i.e. may be important if the contact person is not available 24/7 or an alternate contact may be required.)

ROC.5 ***Describe the key complications from the study drug(s) listed below or study procedure(s):***

The patient might experience sore throat from TEE manipulation for a few hours after the surgery.

ROC.6 ***Any other information that may be important to emergency personnel:***

None

XIII. Other Mod and/or Comments

XIII.1 ***Most modifications should be made in the appropriate section (see Index) of the project itself. If you need to describe other changes, or wish to add comments about something you changed, please do so here.***

CR I. Project Summary

CR I.1 ***Summarize your progress to date in conducting the study at Iowa. Address each of the bulleted items below in your response.***

Describe any problems or delays

Describe any significant changes to the study design (previously approved by the IRB) since the study began (requests for new changes should be described on a Modification form)

Describe any significant subject experiences (benefits, adverse events/adverse reactions) since the last IRB review.

No problems or delays in the study. No changes were made since the study began. No significant subject experiences noted since the last IRB review.

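### VIII.1 names esophageal trauma as the only added physical risk, but no planned data item records it, so the trial has no systematic count of that harm

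*Combined protocol and SAP*

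**What the plan says.** VII.E.6 limits what is taken from the chart. Its scope is set by the opening clause, "When looking at patient medical records, we will only collect the following data", and the items begin: "we will only collect the following data: height, weight, age, any known history of esophageal abnormalities, lesions or disease, current procedure, hemodynamic markers". The rest of the list is the FLACC score after surgery, with the final items read as "postoperatively 24 hours after surgery and total morphine used within 24 hours after surgery". The esophageal item is prior history, which is a baseline characteristic and not an outcome.

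VIII.1 describes the added physical hazard: the "risk involved is an increased risk of esophageal trauma as the TEE probe may be maneuvered more than normal". It presents this as the only extra physical risk and calls it unlikely. ROC.5, which feeds the hospital's research record, names a different complication: "The patient might experience sore throat from TEE manipulation for a few hours after the surgery".

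On monitoring, VIII.2 says "Healthcare professionals will monitor the subject at all times during the operation", and VIII.3 answers No to periodic review of combined data. The aims in I.5 and the analysis in XI.1 cover success rate, tip position and block adequacy. Neither names a safety outcome.

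**The concern.** The form identifies a harm that the study procedure may add, then sets out a restricted chart extraction that does not record it. If the trial is run to that list, a report that no esophageal injury occurred would rest on nobody having been asked to look. This matters because the use is new. VII.B.24 says the device is not FDA-approved for this use, VII.B.35 says the FDA has made no risk assessment, and VII.B.37 says TEE has not been used this way before. The reassurance in VII.B.34 and VII.B.37 comes from routine TEE, whereas VIII.1 says the probe may be moved more than in routine use. The primary success rate is not affected.

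**Working it through.** **Step 1. Is there any place where the harm would be recorded?** The planned data, by source:

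| Source | Items | Adverse-event item? |
|---|---|---|
| Chart extraction (VII.E.6) | Height, weight, age, prior esophageal history, procedure, hemodynamic markers, FLACC, 24-hour morphine | No |
| TEE operator (VII.E.6) | Images before and after threading; tip position relative to the cord | No |
| Anesthesiologist (VII.E.6) | Heart rate and blood pressure response at incision | No |
| Post-operative x-ray (I.5, VII.E.6) | Catheter level | No |
| Analysis (XI.1) | Descriptive statistics on success rate | No |

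The gap therefore does not depend on how widely the word *only* is read. If it governs chart extraction alone, the other sources still hold no adverse event.

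**Step 2. Could the planned extraction carry the item?** Yes. VII.E.6 already draws FLACC and morphine from the record up to 24 hours after surgery, and X.4 keeps the hospital number for chart access. No new visit is needed.

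**Step 3. What would the trial be able to say?** The documents state no safety rate, margin or precision target, so there is no figure of the plan's own to reproduce. The inputs are 20 children with data (VI.15, XI.2) and 25 enrolled (VI.6, XI.2).

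With zero events in n, the exact (Clopper-Pearson) two-sided 95% upper limit is 1 − 0.025^(1/n):

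- n = 20: 1 − 0.025^(1/20) = 16.8%
- n = 25: 1 − 0.025^(1/25) = 13.7%

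The one-sided 95% upper limit is 1 − 0.05^(1/n): 13.9% for n = 20 and 11.3% for n = 25.

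As written, the numerator is not collected, so neither a planned rate nor a limit can be given.

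**Step 4. How likely is it that there would be an event to record?** No rate is in the documents, so a range is assumed. The chance of at least one event is 1 − (1 − p)^n:

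| Assumed true rate p | n = 20 | n = 25 |
|---|---|---|
| 0.1% | 2.0% | 2.5% |
| 1% | 18.2% | 22.2% |
| 5% | 64.2% | 72.3% |
| 10% | 87.8% | 92.8% |

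If injury is as rare as the form suggests, the lower rows do not apply and most likely nothing would be seen. The case for recording it does not depend on which row is true.

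**The case against.** Four stronger readings are tempting, and the documents do not support them.

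- **A broken commitment to test safety.** VII.B.18 asks "Does this project involve testing the safety and/or efficacy of a medical device" and is answered Yes. The question is pre-printed and joined by and/or, so efficacy alone satisfies it. No safety endpoint was promised in I.5 or XI.1.
- **No report of harm is possible.** The continuing-review question (CR I.1) asks about adverse events and is answered, ROC.4 provides a round-the-clock contact for complications, and VIII.2 describes monitoring during the operation. An injury could surface by these routes. None of them sets a definition, a time window or active ascertainment.
- **Nothing is collected after the operating room.** VII.E.6 says "There will be no necessary long-term follow up or data collection. When the patient leaves the operating room, nothing additional is required", but in context this describes what is asked of the subject. The 24-hour chart items show that extraction continues.
- **ROC.5 contradicts VIII.1.** One asks for key complications and the other for risks to subjects. The answers differ mainly in completeness. That calls for alignment and does not show the data-capture gap.

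The strongest objection is to the value of the fix. Every child has TEE clinically and there is no control group (VI.13), so a count cannot separate the extra movement from routine TEE. Sore throat cannot be self-reported by the youngest children, since ages start at 0 (VI.7). Catheter complications are not among the risks that VIII.1 attributes to the study. All of this stands, and it limits the fix to description.

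The part of the form between the reference list and section V, and the consent document, were not available for this review. An item there cannot be ruled out, although VII.E.6 is where the data list sits.

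**Conclusion.** The point holds in a limited form. The plan names one added physical harm and contains no planned, systematic count of it. This is a cheap improvement to what the trial can report. It does not affect the primary analysis or breach a stated safety aim.

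The gain is modest. With zero recorded events the data would still be compatible with a true rate of up to 16.8% (0/20) or 13.7% (0/25), two-sided, so a low rate could not be established. Those limits need only the sample sizes in the form and active ascertainment in every child counted. The event probabilities in the working (2% to 88% for n = 20) rest on assumed rates of 0.1% to 10%.

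**What to change.** 1. Add esophageal injury or bleeding to the VII.E.6 list, with a short definition, taken from the 24-hour chart review already planned. Record it as present, absent or not documented, so that a blank is not read as no event.
2. Add documented sore throat for children able to report it, with its own denominator. Catheter complications are optional.
3. In XI.1, report each item as n/N with an exact 95% confidence interval, where N is all children in whom the probe was moved for the study. State that this is description only, that zero events would leave an upper limit of 16.8% (0/20) or 13.7% (0/25), and that without a control group events cannot be attributed to the extra movement.
4. Separately, align ROC.5 with VIII.1 so that both list the same study-related risks.

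The cost is a few fields and one small table. No visit or procedure is added; the downside is slightly more data entry.
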